#### **Patients entering the single-blind run-in period**

At the time of entry into the single-blind double-dummy placebo run-in period, the site will contact the IVRS/IWRS in order that run-in medication can be assigned and dispensed.

Patient who does not meet the eligibility criteria is considered as screen failure in the study. These patients will be terminated from the study and registered as Screen Failure by using IVRS/IWRS. See Section 3.10.1. Patients cannot be rescreened.

### **Patients entering the double-blind treatment period**

Following completion of the single-blind run-in period, patients eligible for double-blind double-dummy treatment will be randomly assigned to 1 of the 3 treatment arms by the IVRS/IWRS in a 1:1:1 ratio (ticagrelor 10 mg + matching placebo for ticagrelor 45 mg: ticagrelor 45 mg + matching placebo for ticagrelor 10 mg: matching placebo for ticagrelor 10 mg + matching placebo for ticagrelor 45 mg) using a randomisation schedule.

If a patient withdraws from participation in the study, then his/her enrolment/randomisation code cannot be reused.

## **3.4 Procedures for handling incorrectly enrolled or randomised patients**

Patients who fail to meet the eligibility criteria should not, under any circumstances, be enrolled or receive study drug. There can be no exceptions to this rule. Patients who are enrolled, but subsequently found not to meet all the eligibility criteria must not be randomised or initiated on treatment, and must be withdrawn from the study.

Where a patient does not meet all the eligibility criteria but is randomised in error, or incorrectly started on treatment, the following steps to be taken:

- (a) The Investigator or monitor should inform the study physician immediately, ensuring patient safety must always be the number one priority.
- (b) Study Treatment must be discontinued in all cases where continued treatment is deemed to pose a safety risk to the patient. A discussion should occur between the study physician and the Investigator, a decision may be reached that whether to continue or discontinue the patient from study treatment. The study physician must ensure all decisions are appropriately documented. The patient should remain in the study for follow up in accordance with defined study procedures including follow-up on endpoints through the end of the study consistent with the intention-to-treat (ITT) principle.
- (c) In those cases where continuation of study therapy is judged not to present a concern related to safety and disease management, the rationale for continuing study therapy must be clearly documented. The patient should continue follow up in accordance with defined study procedures.

## **3.5 Methods for assigning treatment groups**

The randomisation codes will be computer generated by AZ R&D using the AZ Global Randomisation system (GRand) and loaded into the IVRS/IWRS database. Randomisation

codes will be generated in blocks to ensure approximate balance (1:1:1) between the 3 treatment arms (ticagrelor 10 mg bid, 45 mg bid, or placebo bid).

Randomisation will be done via IVRS/IWRS at Visit 2. The IVRS/IWRS will allocate randomisation codes sequentially within each country as patients become eligible for randomisation. Once a block of randomisation codes is exhausted, the next available block will be allocated by the IVRS/IWRS to the country.

For each patient randomised the IVRS/IWRS will provide the Investigator with a unique kit identification (ID) number matching the treatment arm assigned to the patient. Following randomisation, the first dose of study drug will be administered to the patient as soon as possible. At randomisation and subsequent dispensing visit the patient should always be provided medication with the kit ID(s) allocated by the IVRS/IWRS. If a patient receives the incorrect randomised treatment at any time during the study, this must be corrected as soon as discovered after discussing with study physician.

### **3.6 Methods for ensuring blinding**

This study is double-blind and double-dummy technique will be used. The active tablets and their matching placebo tablets will be provided see Section 7.1 identical in appearance and with the same number and packaging of the tablets. The bottles with IPs will be labelled with unique identification numbers allocated from the IVRS/IWRS, but it will not indicate treatment allocation to the Investigator.

The PRU value obtained from VerifyNow system will be kept strictly blinded to safeguard the integrity of the blinding of Investigators and patients, and hence to minimize any possible bias in data handling.

No member of the study team at AZ or representative, personnel at study centres or any clinical research organisation (CRO) handling data will have access to the randomisation scheme during the conduct of the study, with the exception of the AZ personnel generating the randomisation scheme and the bioanalysis personnel analysing the PK samples as well as AZ Supply Chain, the Patient Safety data entry site and the CRO companies providing the IVRS/IWRS and carrying out the packaging and labelling of IPs. This documentation will be kept in a secure location until the end of the study.

### **3.7 Methods for unblinding**

Individual treatment codes, indicating the treatment randomisation for each randomised patient, will be available to the Investigator(s) or pharmacists from the IVRS/IWRS. Routines for this will be described in the IVRS/IWRS user manual that will be provided to each centre.

The treatment code should not be broken except in medical emergencies when the appropriate management of the patient requires knowledge of the treatment randomisation. The AZ physician or delegate should be consulted whenever possible prior to the Investigator breaking the blind. The Investigator documents and reports the action to AZ, without revealing the treatment given to patient to the AZ staff. The number of individuals at the study site who

become aware of the treatment status should be kept to an absolute minimum including keeping the patient blinded if possible. Treatment with study drug should be continued if considered appropriate.

AZ retains the right to break the code for SAEs that are unexpected and are suspected to be causally related to an IP and that potentially require expedited reporting to regulatory authorities. Treatment codes will not be broken for the planned analyses of data until all decisions on the evaluability of the data from each individual patient have been made and documented.

### **3.8 Restrictions**

The following recommendations will be applied for patients participating in the study:

- Patients may not participate in another clinical study that involves an IP (active or placebo) or device during this study.
- Females of child bearing potential are not allowed to be included in this study unless they use a highly effective method of contraception, and must refrain from becoming pregnant from 1 month following the last dose. A highly effective method is defined as the one which results in a low failure rate (i.e., less than 1% per year) when used consistently and correctly. Examples of highly effective methods include implants, injectables, combined oral contraceptives, some intrauterine devices, sexual abstinence or vasectomised partner. There are no restrictions against fathering a child when treated with ticagrelor. For further details, please see Section 6.6.
- Grapefruit juice must not be consumed during the study.
- Patients are not allowed to eat 2 hours before and 1 hour after dosing at Visit 2 and 3.
- For concomitant medications which are restricted during the study, please see Section 7.7.

### **3.9 Discontinuation of investigational product**

Patients will be discontinued from investigational product (IP) in the following situations:

- Patient decision. The patient is at any time free to discontinue treatment, without prejudice to further treatment
- AE, as judged by Investigator
- Severe non-compliance with the study protocol, as judged by Investigator and/or AZ
- Any major bleeding, as judged by Investigator
- Risk to patient as judged by Investigator

- Pregnancy

**NB.** Discontinuation of IP does not mean discontinuation of follow-up or termination of study participation.

### **3.9.1 Procedures for discontinuation of a patient from IP**

At any time, patients are free to discontinue IP or withdraw from the study (i.e., investigational product and assessments – see Section 3.10 without prejudice to further treatment. A patient that decides to discontinue IP will always be asked about the reason(s) and the presence of any AEs. If possible, they will be seen and assessed by an Investigator(s). All end of treatment (Visit 5) procedures will be followed in addition to safety follow-up (Visit 6). AEs will be followed up (see Section 6); electronic devices for Patient Reported Outcomes (ePRO) and all study drugs should be returned by the patient.

If a patient is withdrawn from study, see Section 3.10.

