#### **4.2.4 Visit 5, End of treatment visit**

- Patient eDiary will be collected
- Review concomitant medications and AEs including bleeding events
- Obtain vital signs (pulse rate and BP), body weight
- Perform standard physical examination
- Obtain specimens (blood) for safety laboratory panel
- Obtain specimen for urinalysis and perform urine pregnancy test for females of child bearing potential
- Collect and assess compliance with study drug based on tablet count

Instruct the patient that they will be contacted for safety assessment through telephone after 2 weeks.

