### **8.3 Definitions of analysis sets**

#### **8.3.1 Efficacy analysis set**

All randomised patients with at least 1 eDiary record post-dose will be included in the efficacy analysis set. Patients will be analysed according to their randomised study drug.

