## **8.4 Outcome measures for analyses (Not Applicable)**

### **8.5 Methods for statistical analyses**

No statistical comparisons are planned for the primary objective. PRO and safety measures will be summarized descriptively using respective analysis set.

In general, all efficacy, safety, plasma concentrations of ticagrelor and active metabolite, PRU and PRO variables will be presented using descriptive statistics and graphs as appropriate. Continuous variables will be presented with descriptive statistics (n, mean, standard deviation [SD], median, min, max), within treatment group. Geometric mean and coefficient of variation (CV) will be used instead of arithmetic mean and SD, if appropriate, with CV(%) calculated as:

$$100 \cdot \sqrt{(\exp(s^2) - 1)}$$

where s is the SD of the data on a log scale.

Categorical variables will be summarized in frequency tables (number of patients and percentage), by treatment group. Data will also be presented in individual patient listings.

The presentation of pain, intensity of pain and days of analgesic use due to SCD, will be presented by week. They will also be presented by subgroup of PGIC, divided into 3 groups, improved (1 and 2), no change (3, 4 and 5) and worse (6 and 7).

In general, baseline values will be the closest observation prior to the first administration of randomised IP. For the baseline value of pain, intensity of pain and days of analgesic use, a mean value for the 4 weeks in the Screening period will be calculated.

The number of days with pain due to SCD and the analysis of analgesic use due to SCD will be analysed using an ANCOVA model, with treatment, country, baseline average value, and baseline hydroxyurea (HU) use as explanatory variables, and treatment and HU as fixed effects and centre as a random effect. Least squares differences in means between ticagrelor 45 mg and placebo and ticagrelor 10 mg and placebo with corresponding 90% confidence interval will be presented. The objectives will be analysed as a proportion of days, during the whole treatment period. A sensitivity analysis of pain and analgesic use will be performed using the ANCOVA model but excluding country and baseline HU use.

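### Section 3.9.1 has patients who stop study drug return the eDiary, so recording of the primary endpoint stops with the drug although Section 3.9 says participation continues

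*Protocol*

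**What the plan says.** Protocol Section 3.9 lists the reasons for stopping IP and closes with a note: "Discontinuation of IP does not mean discontinuation of follow-up or termination of study participation".

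Section 3.9.1 gives the procedure. It first separates a patient who discontinues IP from one who withdraws from the study, which it glosses as giving up both IP and assessments. For the patient who only stops IP, it prescribes all Visit 5 procedures plus the Visit 6 safety contact, and states that "electronic devices for Patient Reported Outcomes (ePRO) and all study drugs should be returned by the patient". Among the Visit 5 procedures in Section 4.2.4 is "Patient eDiary will be collected". Section 3.10.2 asks for the same device return when consent is withdrawn.

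Section 3.4(b), on patients randomised or started on treatment in error, keeps them in the study with "follow-up on endpoints through the end of the study consistent with the intention-to-treat (ITT) principle".

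Section 5.1.1.1 collects pain each evening in the eDiary from enrolment to end of treatment. It does not say whether that means the patient's last dose or scheduled Week 12. Section 5.1.1.2 puts the daily analgesic question on the same device.

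On analysis, Section 8.3.1 says "All randomised patients with at least 1 eDiary record post-dose will be included in the efficacy analysis set", with patients analysed by randomised drug, and Section 8.5 says "The objectives will be analysed as a proportion of days, during the whole treatment period".

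**The concern.** The instruction to sites and the planned analysis do not fit together. If the diary goes back when the drug does, the later part of the 12 weeks is empty for every patient who stops early. The whole-period proportion for that patient can then rest only on days up to stopping.

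This matters because stopping need not be unrelated to treatment or outcome. Section 3.9 names adverse events, major bleeding and patient decision as reasons, and Sections 1.3 and 3.9.2 describe dyspnoea with ticagrelor. Arms of 30 leave little room, and Section 3.10.2 says withdrawn patients are not replaced. The gap arises in data collection, so later imputation would rest on assumptions that the trial's own data cannot test.

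**Working it through.** **Passages side by side**

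| Question | Text | Implication |
|---|---|---|
| Does participation end when IP stops? | 3.9, note | No |
| Who gives up assessments? | 3.9.1 and 3.10.2 | Only those who withdraw from the study |
| What happens to the diary when IP stops? | 3.9.1 and 4.2.4 | Collected or returned, alongside the drug |
| What happens at consent withdrawal? | 3.10.2 | The same device return |
| Is there another source of daily pain? | 5.1.1.1 | None |
| Which period is analysed? | 8.3.1 and 8.5 | Whole treatment period, as randomised |

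The third row conflicts with the first two. For the primary endpoint, stopping drug and leaving the study are handled alike. The conflict is sharpest under 3.4(b): a patient randomised in error and taken off treatment is owed endpoint follow-up, yet under 3.9.1 returns the only instrument that records the endpoint.

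**The plan's own figure**

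Inputs from Section 8.2: 30 per group, SD 0.4, 90% confidence interval, difference 0.17.

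Half-width = 1.645 × 0.4 × √(2/30) = 0.1699, which reproduces the stated 0.17.

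**Illustration of size**

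Assumptions, none from the protocol: the on-drug difference is 0.17; a share *q* of the active arm stops at week *w* of 12; the effect is lost from then on; stopping is unrelated to pain. The difference over all 12 weeks is then

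0.17 × [(1 − *q*) + *q* × *w*/12]

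- *q* = 10%, *w* = 6: 0.17 × (0.90 + 0.050) = 0.1615
- *q* = 20%, *w* = 4: 0.17 × (0.80 + 0.067) = 0.147
- *q* = 30%, *w* = 4: 0.17 × (0.70 + 0.100) = 0.136

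Diary days not recorded per active arm, out of 30 × 84 = 2520:

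- 3 patients × 42 days = 126
- 6 patients × 56 days = 336
- 9 patients × 56 days = 504

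The gaps from 0.17 are about 0.009, 0.023 and 0.034. Each is small beside the half-width of 0.17. The illustration does not cover selective stopping, where patients stop because of pain or a drug effect. That bias could go in either direction and cannot be sized from the protocol.

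**The case against.** The strongest reply is that Sections 3.9 and 3.9.1 can stand together. The protocol calls its post-treatment phase the follow-up period, and in Sections 1.4 and 4.3 that means the Visit 6 safety call. The Section 3.9 note mentions neither endpoints nor the diary. Section 3.9.1 says the device should be returned but gives no date, so Visit 5 could be imagined at its scheduled Week 12. An on-treatment symptom endpoint is also defensible in a phase IIb study of 30 per arm for which Section 8.5 plans no statistical comparisons on the primary objective.

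Part of this stands. Immediate return is the likelier reading, not the only one. But Section 3.9.1 is the procedure for stopping IP, pairs the device with the drug and leaves only Visit 6 afterwards. No text provides for keeping the diary. Reading follow-up as the safety call does not explain the rest of the note, which says participation continues too. At best the rule is unclear and sites could apply it differently. An on-treatment endpoint would have to be declared, and Section 8.5 describes the whole treatment period.

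Three stronger readings are tempting but not supported:

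- **That the protocol requires intention-to-treat endpoint follow-up for everyone who stops IP.** That sentence is in Section 3.4(b) and covers only patients randomised or started on treatment in error. For others the basis is the Section 3.9 note and the distinction between stopping IP and giving up assessments.
- **That the result would be biased upwards by 5% to 25%**, the ratios of 0.17 to the three figures above. Those are gaps between two different quantities, on-drug and whole-period, under assumed stopping rates. They are not demonstrated bias.
- **That short diaries receive damaging weight because one record admits a patient to the efficacy set.** Handling of incomplete diaries belongs to the SAP, which is not at hand. With an SD of about 0.4 in Section 8.2, differences between patients probably dominate the extra noise of a short diary.

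**Conclusion.** The point holds as an internal conflict in the data-collection rules. As written, Section 3.9.1 most naturally ends diary recording when IP stops, against the Section 3.9 note, against its own distinction between stopping IP and withdrawing from assessments, and, for patients randomised in error, against Section 3.4(b). For patients who stop early, an as-randomised whole-period comparison becomes an on-treatment one.

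Its size is unknown. A whole-period difference of about 0.16 to 0.14 against an on-drug 0.17 depends entirely on the assumed 10% to 30% stopping at weeks 4 to 6, loss of effect afterwards, and stopping unrelated to pain. The conflict itself needs none of these figures. This should be fixed: the likely effect is moderate, but unrecorded days cannot be recovered at analysis.

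**What to change.** Amend the protocol as follows:

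1. In Section 3.9.1, have patients who stop IP without withdrawing consent return only study drug, keep the eDiary and complete it daily to scheduled Week 12. Make the collection step in Section 4.2.4 consistent with this.
2. In Section 5.1.1.1, define end of treatment, for diary collection, as scheduled Week 12 rather than last dose.
3. In Section 8.5, state that diary days on or off drug enter the primary proportion.
4. Keep device return for withdrawal of consent in Section 3.10.2.

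The cost is amendment wording, longer use of some devices and a modest diary burden for patients off drug. If the sponsor prefers an on-treatment endpoint, the protocol should say so openly, and Sections 3.4(b), 3.9 and 8.5 should be brought into line with it.

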### **3.9.2 Procedure for management of dyspnea associated with investigational product**

If a patient develops new, prolonged, or worsened dyspnea during treatment with ticagrelor, exclude underlying diseases that may require treatment. If dyspnea is determined to be related to ticagrelor, no specific treatment is required.

### **3.9.3 Procedure for management of elevated serum creatinine**

Serum creatinine may initially increase and then decrease on continued treatment. These increases typically do not progress with ongoing treatment and often decrease with continued therapy.

If a 50% increase in serum creatinine is observed, the patient should be monitored closely, but this value may decrease with continued therapy. However, if the serum creatinine is 2x ULN and other causes are ruled out and the value does not improve on continued therapy, then discontinuation should be considered.

### **3.9.4 Procedure for management of elevated liver function tests**

Subjects with grade 3 elevations in liver function tests (LFTs; >5x ULN) should have their LFTs repeated. If LFTs remain >5x ULN, and/or elevated total bilirubin >2 mg/dl (and sickle cell-related causes are excluded) and thought to be related to ticagrelor, stopping the study drug should be considered.

## **3.10 Criteria for withdrawal**

### **3.10.1 Screen failures**

Screening failures are patients who do not fulfil the eligibility criteria for the study, and therefore must not be randomised. These patients should have the reason for study withdrawal recorded as 'Eligibility criteria not fulfilled' (i.e., patient does not meet the required inclusion/exclusion criteria). This reason for study withdrawal is only valid for screen failures (not randomised patients).

### **3.10.2 Withdrawal of the informed consent**

Patients are free to withdraw from the study at any time (IP and assessments), without prejudice to further treatment.

A patient who withdraws consent will always be asked about the reason(s) and the presence of any AEs. The Investigator will follow up AEs outside of the clinical study. The patient will return ePRO devices.

If a patient withdraws from participation in the study, then his/her enrolment/randomisation code cannot be reused. Withdrawn patients will not be replaced after randomisation.

### **Withdrawal of informed consent for donated biomarker samples**

As collection of the blood biomarker samples is a voluntary part of the study, if patients withdraw consent for use then the patient may continue in the study. Patients may withdraw from optional exploratory research at any time, without prejudice to further treatment and independent of any decision concerning participation in other aspects of the main study. Procedures for withdrawal from the exploratory research are outlined in Section [5.7.4](#).

### **3.11 Discontinuation of the study**

The study may be stopped if, in the judgment of AZ, trial patients are placed at undue risk because of clinically significant findings that:

- Are assessed as causally related to study drug,
- Are not considered to be consistent with continuation of the study

Regardless of the reason for termination, all data available for the patient at the time of discontinuation of follow-up must be recorded in the electronic case report form (eCRF). All reasons for discontinuation of treatment must be documented.

In terminating the study, the Sponsor will ensure that adequate consideration is given to the protection of the patients' interests.

#### 4. STUDY PLAN AND TIMING OF PROCEDURES

**Table 1 Study Plan Detailing the Procedures**

Study Period	Screening period	Treatment period				Follow-up period	For details see Protocol Section
Visit	Enrolment	Randomisation	Treat-ment	Treat-ment	End of treatment	Phone contact	
Visit Number	1	2	3	4 a	5	6	
Week	-4	0	1	4	12	14	
Day	-28	0	7	28	84	98	
Visit Window	-35 to -28	Not Applicable	±3 days	±7 days	±7 days	±7 days	
Signed and Dated Informed consent	✓						10.4
Inclusion/Exclusion Criteria	✓	✓ b					3.1 and 3.2
Allocation of E-code via IVRS/IWRS	✓						3.3
Randomisation via IVRS/IWRS		✓					3.3 and 3.5
Electronic Diary Assessment c : – Pain (worst/ average/ right now), daily – Analgesic use, daily – Absence school/ work, weekly – PGIC, end of treatment							5.1.1
Medical and Surgical History	✓						4.1
Demographics	✓						4.1
Vital Signs (BP and Pulse Rate)	✓	✓	✓	✓	✓		5.2.4
Weight and Height	✓				✓ d		5.2.4
Physical Examination	✓				✓		5.2.2
12-Lead ECG	✓						5.2.3
Ophthalmology examination (if not performed within previous 12 months)	✓						4.1

Study Period	Screening period	Treatment period				Follow-up period	For details see Protocol Section
Visit	Enrolment	Rando-misation	Treat-ment	Treat-ment	End of treatment	Phone contact	
Visit Number	1	2	3	4 a	5	6	
Week	-4	0	1	4	12	14	
Day	-28	0	7	28	84	98	
Visit Window	-35 to -28	Not Applicable	±3 days	±7 days	±7 days	±7 days	
Blood samples for Hematology and Clinical Chemistry	✓			✓	✓		5.2.1
Blood samples for coagulation (INR and PTT)	✓						5.2.1
Virology screen (HIV, HBsAg, and HCV)	✓						5.2.1
Urinalysis (dipstick)	✓			✓	✓		5.2.1
Pregnancy Test e	✓	✓		✓	✓		5.2.1
Platelet aggregation (PRU) (VerifyNow) f		✓	✓				5.5.1
Blood sampling for Biomarkers (optional)		✓ g	✓	✓			5.7
Blood sampling for Pharmacokinetics h		✓	✓				5.4
Dispense IP	✓ i	✓		✓			7
Administration of IP in Clinic	✓ i	✓	✓				7
Return IP and Drug Accountability		✓		✓	✓		7.5 and 7.6
Vaso-occlusive crisis	✓ j	✓	✓	✓	✓		5.1.2
Concomitant Medications	✓	✓	✓	✓	✓	✓	7.7
Adverse Event review (AEs and SAEs) including bleeding events	✓	✓	✓	✓	✓	✓	6

AE adverse event; β-hCG beta-human chorionic gonadotropin; BP blood pressure; ECG electrocardiogram; HBsAg hepatitis B surface antigen; HCV hepatitis C virus; HIV human immunodeficiency virus; INR international normalized ratio; IVRS Interactive Voice Response System; IWRS Interactive Web Response System; IP investigational product; PTT Partial Thromboplastin Time; SAE serious adverse event.

a Patients should be contacted by telephone between Visits 4 and 5 (at Week 8 at a minimum), and Investigators are expected to follow subjects per local institutional guidelines during this period. If unscheduled visits are required for AEs or medical complications, please see Section 4.2.5.

b Confirm patient still meets inclusion and exclusion criteria prior to receiving first dose of study drug.

c Electronic diary will be dispensed to patient at Visit 1.

d Only weight will be measured.

- e For females of child bearing potential. At Screening (Visit 1), serum  $\beta$ -hCG; at all other visits, urine dipstick.
- f PRU will be assessed at 0 (pre-dose) and 2 hours post-dose at Visits 2 and 3.
- g Optional Biomarker sample needs to be collected only if patient agrees to consent for additional optional Biological Samples Research Addendum to Informed Consent Form. Blood sample must be taken prior to first dose of study drug at Visit 2.
- h PK will be measured 2 hours post-dose at Visit 2, and at 0 (pre-dose) and 2 hours post-dose at Visit 3.
- i At Screening, patients will be given matching placebo tablets for the 10 mg and 45 mg doses and starting at Visit 2, patients will be randomly assigned to 1 of 3 treatment regimens.
- j At Screening, history of VOC over previous 12 months will be recorded.

